9.2.3. Criteria for Evaluation

The primary objective will be to evaluate the change from baseline in wrinkle dimensions in the crow's feet area for the test product compared to no treatment after 4 weeks of twice daily product application. Given that this is a POC study, the study will be considered a success if at least a trend in favour of the test product is observed. There will be no adjustment to the critical alpha level of 0.05 to account for inflation due to multiplicity. P-values resulting from inferential testing will be considered primarily as summary statistics.

9.2.4. Handling of Dropouts and Missing Data

Missing data will not be replaced or imputed. Dropouts will be included in analyses up to the point of discontinuation.

9.3. Statistical Methods and Analytical Plan

Additional details of the proposed statistical analysis will be documented in the statistical analysis plan (SAP), which will be written following finalisation of the protocol and prior to study unblinding / analysis (as appropriate) and performed by GSK.

9.3.1. Demographic and Baseline Characteristics

Age and baseline Fitzpatrick wrinkle assessment scores will be summarised descriptively using means, medians and standard deviations. Race and Fitzpatrick skin type scores will be summarised using frequency counts and percentages.

Document Name	Clinical Protocol 207468.doc		
Type	Version	Document Identifier	Effective Date
eldo_controlled	3.0; Most-Recent; Effective; CURRENT	090032d580d15804	24-Mar-2017 07:31:33
Reason For Issue	Auto Issue		

9.3.2. Primary Analysis(es)

All efficacy analyses will be performed on the intent to treat (ITT) population.

Baseline and change from baseline in DermaTOP parameters R_a , R_z , S_a and S_{tm} will be summarised (N, mean, standard deviation, median, minimum and maximum) by treatment arm (test product, Olay ProX Wrinkle Smoothing Cream, no treatment) for each study visit (weeks 2 and 4). For each parameter, test product versus no treatment and positive control versus no treatment will be compared for the change from baseline at 2 weeks, and 4 weeks (primary endpoint), using analysis of covariance (ANCOVA) with subject (random effect), treatment, and side of face as main effects and baseline value as covariate. This approach allows for the inclusion of data from all subjects treated with a given treatment arm (test product, positive control or no treatment) regardless of the treatment group (test product/no treatment, test product/positive control, positive control/no treatment) to which they were randomised to derive estimates of treatment effect.

If the assumption of normality is rejected, an appropriate transformation to the data will be performed to facilitate the above method of analysis. Least square means from the ANCOVA model for the change from baseline will be presented for each treatment arm and pairwise treatment comparison, together with the 95% confidence intervals. In the absence of an appropriate data transformation, non-parametric analysis will be performed.

9.3.3. Secondary Analysis(es)

The same presentation and analysis methods, as outlined above, will be performed using change from baseline for other parameters; clinical wrinkle assessment, TEWL values, Corneometer values and Cutometer parameters R5 and R7. The texture assessment resulting from the ranking of photos will inherently be an assessment of change from baseline. As such, the data resulting from these rankings will be tabulated by treatment arm as proportions with baseline image better and Day 29 image better and analysed using a logistic regression.

9.3.4. Safety Analysis(es)

Adverse Events (AE) will be tabulated according to the current version of the Medical Dictionary for Regulatory Activities (MedDRA). Frequencies and percentages will be presented by treatment arm overall, for each system organ class,

Document Name	Clinical Protocol 207468.doc		
Type	Version	Document Identifier	Effective Date
eldo_controlled	3.0; Most-Recent; Effective; CURRENT	090032d580d15804	24-Mar-2017 07:31:33
Reason For Issue		Auto Issue	

and for each preferred term. Summaries of treatment-emergent AE's, treatment-related AEs, AEs leading to discontinuation, and serious AEs will be completed.

Document Name	Clinical Protocol 207468.doc		
Type	Version	Document Identifier	Effective Date
eldo_controlled	3.0; Most-Recent; Effective; CURRENT	090032d580d15804	24-Mar-2017 07:31:33
Reason For Issue	Auto Issue		

10. STUDY GOVERNANCE CONSIDERATIONS

10.1. Posting of Information on Publicly Available Clinical Trials Registers

Study information from this protocol will be posted on publicly available clinical trial registers before enrolment of subjects begins.

10.2. Regulatory and Ethical Considerations, Including the Informed Consent

The study will be conducted in accordance with all applicable regulatory requirements, and with GSK policy.

The study will also be conducted in accordance with ICH Good Clinical Practice (GCP), all applicable subject privacy requirements, and the guiding principles of the current version of the Declaration of Helsinki. This includes, but is not limited to, the following:

- Before initiating a trial, the investigator/institution should have written and dated approval/favourable opinion from the IEC for the trial protocol (including amendments), written informed consent form, consent form updates, subject recruitment procedures (e.g., advertisements), investigator brochure/ safety statement (including any updates) and any other written information to be provided to subjects. A letter or certificate of approval will be sent by the investigator to the sponsor prior to initiation of the study, and also when subsequent amendments to the protocol are made.
- Signed informed consent to be obtained for each subject before participation in the study (and for amendments as applicable)
- Investigator reporting requirements (e.g. reporting of AEs/SAEs/protocol deviations to IEC)
- GSK will provide full details of the above procedures, either verbally, in writing, or both.

 GlaxoSmithKline	Document Name	Clinical Protocol 207468.doc		
	Type	Version	Document Identifier	Effective Date
	eldo_controlled	3.0; Most-Recent; Effective; CURRENT	090032d580d15804	24-Mar-2017 07:31:33
	Reason For Issue	Auto Issue		

10.3. Quality Control (Study Monitoring)

In accordance with applicable regulations including GCP, and GSK procedures, GSK or designee (i.e. third party vendor) monitors will contact the site prior to the start of the study to review with the site staff the protocol, study requirements, and their responsibilities to satisfy regulatory, ethical, and GSK requirements.

When reviewing data collection procedures, the discussion will include identification, agreement and documentation of data items for which the CRF will serve as the source document.

GSK or designee will monitor the study and site activity to verify that the:

- Data are authentic, accurate, and complete.
- Safety and rights of subjects are being protected.
- Study is conducted in accordance with the currently approved protocol and any other study agreements, GCP, and all applicable regulatory requirements.

The extent and nature of monitoring will be described in a written monitoring plan on file at GSKCH. The investigator (or designee) agrees to allow the monitor direct access to all relevant documents and agrees to co-operate with the monitor to ensure that any problems detected in the course of these monitoring visits are resolved.

10.4. Quality Assurance

To ensure compliance with GCP and all applicable regulatory requirements, GSK may conduct a quality assurance assessment and/or audit of the site records, and the regulatory agencies may conduct a regulatory inspection at any time during or after completion of the study.

In the event of an assessment, audit or inspection, the investigator (and institution) must agree to grant the advisor(s), auditor(s) and inspector(s) direct access to all relevant documents and to allocate their time and the time of their staff to discuss the conduct of the study, any findings/relevant issues and to implement any corrective and/or preventative actions to address any findings/issues identified.

The sponsor will be available to help investigators prepare for an inspection.

Document Name	Clinical Protocol 207468.doc		
Type	Version	Document Identifier	Effective Date
eldo_controlled	3.0; Most-Recent; Effective; CURRENT	090032d580d15804	24-Mar-2017 07:31:33
Reason For Issue	Auto Issue		

10.5. Conditions for Terminating the Study

Upon completion or premature discontinuation of the study, the GSKCH monitor will conduct site closure activities with the investigator or site staff, as appropriate, in accordance with applicable regulations including GCP, and GSKCH Standard Operating Procedures.

Both GSKCH and the Investigator reserve the right to temporarily suspend or prematurely discontinue this study at any time for reasons including, but not limited to, safety or ethical issues or severe non-compliance. For multicenter studies (if applicable), this can occur at one or more or at all sites.

If the trial is prematurely terminated or suspended for any reason, the investigator site should promptly inform the trial subjects and should assure appropriate therapy/ follow-up for the subjects. Where required by the applicable regulatory requirements, GSKCH should inform the regulatory authority (ies).

In addition:

- If the investigator terminates or suspends a trial without prior agreement of GSKCH, the investigator site should promptly inform the sponsor and the IEC, and should provide the sponsor and the IEC a detailed written explanation of the termination or suspension.
- If the GSKCH terminates or suspends a trial, the investigator should promptly inform the IEC and provide the IEC a detailed written explanation of the termination or suspension.
- If the IEC terminates or suspends its approval/favourable opinion of a trial, the investigator should promptly notify the GSKCH and provide GSKCH with a detailed written explanation of the termination or suspension.

10.6. Records Retention

Following closure of the study, the investigator must maintain all site study records (except for those required by local regulations to be maintained elsewhere), in a safe and secure location.

The records (study/ site master file) must be maintained to allow easy and timely retrieval, when needed (e.g., for a GSK audit or regulatory inspection) and must be available for review in conjunction with assessment of the facility, supporting systems, and relevant site staff.

 GlaxoSmithKline	Document Name	Clinical Protocol 207468.doc		
	Type	Version	Document Identifier	Effective Date
	eldo_controlled	3.0; Most-Recent; Effective; CURRENT	090032d580d15804	24-Mar-2017 07:31:33
	Reason For Issue	Auto Issue		

Where permitted by local laws/regulations or institutional policy, some or all of these records can be maintained in a format other than hard copy (e.g., microfiche, scanned, electronic); however, caution needs to be exercised before such action is taken.

The investigator must ensure that all reproductions are legible and are a true and accurate copy of the original and meet accessibility and retrieval standards, including re-generating a hard copy, if required. Furthermore, the investigator must ensure there is an acceptable back-up of these reproductions and that an acceptable quality control process exists for making these reproductions.

The investigator must assure that the subject's anonymity will be maintained. On CRFs or other documents submitted to GSKCH, subjects should not be identified by their names or initials, but by an identification code. The investigator should keep a separate log of subjects' codes, names and addresses. Documents not for submission to GSKCH, e.g. subjects' written consent forms, should be maintained by the investigator in strict confidence.

GSK will inform the investigator of the time period for retaining these records to comply with all applicable regulatory requirements (GSKCH recommends that documents be kept for 10 years). The investigator is also required to keep subject identification codes on file for at least 15 years after completion or discontinuation of the study. The minimum retention time will meet the strictest standard applicable to that site for the study, as dictated by any institutional requirements or local laws or regulations, GSK standards/procedures, and/or institutional requirements.

No study document should be destroyed without a prior written agreement between GSKCH and the investigator. The investigator must notify GSK of any changes in the archival arrangements, including, but not limited to, archival at an off-site facility or transfer of ownership of the records in the event the investigator is no longer associated with the site.

10.7. Provision of Study Results to Investigators, posting of Information on Publicly Available Clinical Trials Registers and Publication

Where required by applicable regulatory requirements, an investigator signatory will be identified for the approval of the clinical study report. The investigator will be provided reasonable access to statistical tables, figures, and relevant reports and will

Document Name	Clinical Protocol 207468.doc		
Type	Version	Document Identifier	Effective Date
eldo_controlled	3.0; Most-Recent; Effective; CURRENT	090032d580d15804	24-Mar-2017 07:31:33
Reason For Issue		Auto Issue	

have the opportunity to review the complete study results at a GSK site or other mutually-agreeable location.

GSK will also provide the investigator with the full summary of the study results. The investigator is encouraged to share the summary results with the study subjects, as appropriate.

The procedures and timing for public disclosure of the results summary and for development of a manuscript for publication will be in accordance with GSK Policy.

A manuscript will be progressed for publication in the scientific literature if the results provide important scientific or medical knowledge.

Document Name	Clinical Protocol 207468.doc		
Type	Version	Document Identifier	Effective Date
eldo_controlled	3.0; Most-Recent; Effective; CURRENT	090032d580d15804	24-Mar-2017 07:31:33
Reason For Issue	Auto Issue		

12. APPENDICES

12.1. Appendix 1 - Abbreviations and Trademarks

Abbreviations

µl	Microlitres
AE	Adverse Event
ANCOVA	Analysis of Covariance
ATP	Adenosine Tri-Phosphate
AUC	Area under Curve
CCD	charge coupled device
CD	Compact Disc
cm ²	Centimetre squared
CFR	Code of Federal Regulations
CRF	Case Report Form
DVD	Digital Versatile Disc
EDC	Electronic Data Capture
EEMCO	European Expert Group on Efficacy Measurement of Cosmetics and Other Topical Products
DIN EN ISO	Deutsches Institut für Normung (German institute for norms) EN= European Norm; ISO= International Organization for Standardisation
FOV	Field Of View
GCP	Good Clinical Practice
g	Gram
GSKCH	GlaxoSmithKline Consumer Healthcare
ICH	International Conference on Harmonization of Technical Requirements for Registration of Pharmaceuticals for Human Use
ICF	Informed Consent Form
IEC	Independent Ethics Committee
ITT	Intention to Treat
LCD	Liquid Crystal Display
LSLV	Last Subject Last Visit

Document Name	Clinical Protocol 207468.doc		
Type	Version	Document Identifier	Effective Date
eldo_controlled	3.0; Most-Recent; Effective; CURRENT	090032d580d15804	24-Mar-2017 07:31:33
Reason For Issue	Auto Issue		

hr	Hour
mg	milligrams
mL	millilitre
mm	millimetre
MYSQL	Michael Widenius Structured Query Language
NADH	Nicotinamide adenine dinucleotide phosphate
OTC	Over The Counter
PC	Personal Computer
PII	Personally Identifiable Information
PP	Per Protocol
POC	Proof of Concept
SAE	Serious Adverse Event
SAP	Statistical Analysis Plan
SC	Stratum Corneum
TEWL	Transepidermal Water Loss
VRS	Visual Rating Scale
UV	Ultraviolet
3D	Three Dimensional

[figure not shown]
 GlaxoSmithKline	Document Name	Clinical Protocol 207468.doc		
Type	Version	Document Identifier	Effective Date	
eldo_controlled	3.0; Most-Recent; Effective; CURRENT	090032d580d15804	24-Mar-2017 07:31:33	
Reason For Issue	Auto Issue			

12.2. Appendix 2 - Fitzpatrick Skin Type

CCI

CCI

[figure not shown]

Document Name	Clinical Protocol 207468.doc		
Type	Version	Document Identifier	Effective Date
eldo_controlled	3.0; Most-Recent; Effective; CURRENT	090032d580d15804	24-Mar-2017 07:31:33
Reason For Issue	Auto Issue		

12.3. Appendix 3 – Fitzpatrick Wrinkle Score (Crow’s Feet Area)

Fitzpatrick Wrinkle Score

CCI

[figure not shown]

Document Name	Clinical Protocol 207468.doc		
Type	Version	Document Identifier	Effective Date
eldo_controlled	3.0; Most-Recent; Effective; CURRENT	090032d580d15804	24-Mar-2017 07:31:33
Reason For Issue	Auto Issue		

proDERM 

CCI

 GlaxoSmithKline	Document Name	Clinical Protocol 207468.doc	Document Identifier	Effective Date
	Type	Version		
eldo_controlled		3.0; Most-Recent; Effective; CURRENT	090032d580d15804	24-Mar-2017 07:31:33
	Reason For Issue	Auto Issue		

12.4. Appendix 4 – Texture Ranking Scale

[figure not shown]

## Glossary

CI	Confidence Interval
ITT	Intent-to-Treat
PP	Per Protocol
AE	Adverse Event
MedDRA	Medical Dictionary for Regulatory Activities
TE	Treatment Emergent
TEWL	Transepidermal Water Loss

Document Name	Statistical Analysis CCI	207468.docx	
Type	Version	Document Identifier	Effective Date
eldo_clinical_doc	1.0; CURRENT; Most-Recent; Effective	090032d580d23463	10-Apr-2017 13:34:23
Reason For Issue	Auto Issue		

## 1 Introduction

This document describes the statistical methods and data presentations to be used in the summary and analysis of the final data from Protocol 207468.

## 2 Objectives

Objectives	Endpoints
Primary	
Evaluation of wrinkle dimensions (change from baseline) of test product compared to no treatment on the Periocular / Crow's Feet Area.	DermaTOP parameter $R_a$ at 4 weeks.
Secondary	
Evaluation of wrinkle dimensions (change from baseline) of test product and positive control compared to no treatment in the Periocular / Crow's Feet Area.	DermaTOP parameter $R_a$ at 2 weeks and 4 weeks (positive control only)
	DermaTOP parameters $R_z$ , $S_a$ and $S_{tm}$ at 2 and 4 weeks
	Clinical Fitzpatrick Wrinkle Score at 2 and 4 weeks
Evaluation of skin moisturisation (change from baseline) of test product and positive control compared to no treatment on the Sub-ocular/ Cheek Area.	Instrumental Corneometer values at 2 and 4 weeks
Evaluation of texture (change from baseline) of test product and positive control compared to no treatment on the full face.	Texture ranking at 4 weeks
Evaluation of skin elasticity (change from baseline) of test product and positive control compared to no treatment on the Sub-ocular/ Cheek Area.	Instrumental Cutometer parameters $R5$ and $R7$ at 2 and 4 weeks
Evaluation of skin barrier (change from baseline) of test product and positive control compared to no treatment on the Sub-ocular/ Cheek Area.	Instrumental Trans-Epidermal Water Loss (TEWL) values at 2 and 4 weeks
To evaluate the general safety of the study products	Assessment of frequency and severity of Adverse Events (AEs)

Document Name	Statistical Analysis CCI	207468.docx	
Type	Version	Document Identifier	Effective Date
eldo_clinical_doc	1.0; CURRENT; Most-Recent; Effective	090032d580d23463	10-Apr-2017 13:34:23
Reason For Issue	Auto Issue		

### 3 Study Design

- Evaluator-blind
- Single study centre
- Split-face design
- Healthy female subjects aged 30 to 65 with self-reported sensitive skin and visible signs of aging (visual wrinkles) on the face
- Study treatments: Positive- (Olay ProX Wrinkle Smoothing Cream) and Untreated-control
- Randomisation was to two of the 3 treatment arms (test product, positive control, no treatment) with treatment arm assignment further randomised to either the right side or left side of the face. Therefore, a subject was randomised to one of the 6 possible treatment groups:

Right Side of Face	Left Side of Face
Test Product	Positive Control
Test Product	No Treatment
Positive Control	No Treatment
Positive Control	Test Product
No Treatment	Test Product
No Treatment	Positive Control

### 4 Sample Size Determination

Approximately 90 healthy subjects will be screened to randomise at least 72 subjects to ensure 66 subjects complete the entire study. This will ensure approximately 44 subjects per treatment arm (test product, positive control, no treatment) or 22 per treatment group (test product/no treatment, test product/positive control, positive control/no treatment).

Document Name	Statistical Analysis CCI	207468.docx	
Type	Version	Document Identifier	Effective Date
eldo_clinical_doc	1.0; CURRENT; Most-Recent; Effective	090032d580d23463	10-Apr-2017 13:34:23
Reason For Issue	Auto Issue		

The sample size is based on clinical considerations. With 40 subjects, a difference between test product and untreated in the change from baseline in  $R_a$  of at least 46% of the magnitude of the within-subject standard deviation of the difference would be detectable at two-sided alpha=0.05 with approximately 80% power.

## 5 Data Considerations

### 5.1 Analysis Populations

- The 'Intent to treat' (ITT) population includes all subjects who are randomised into the study and have at least one post-baseline clinical assessment available. All efficacy analyses will be based on the ITT population.
- The Safety population will include all subjects with at least one product application to either side of the face. All safety analyses will be performed using the Safety population.
- The Per Protocol (PP) population will consist of the subset of ITT subjects which excludes those subjects with significant protocol deviations. Protocol deviations will be identified prior to database unblinding and will include, but not be limited to, non-compliance with the protocol or product application and use of prohibited concomitant medications. Confirmatory analyses of at least the primary efficacy endpoint of DermaTOP  $R_a$  and key secondary objective relating to Fitzpatrick wrinkle score will be performed on the PP population.

Subjects with a protocol violation that is deemed to affect facial skin assessments after a specific timepoint will be part of the PP population, but will have their data excluded from the assessment at which the protocol violation occurred.

Violations that may lead to the exclusion of data for PP analysis include, but are not limited to, the following:

- Violation of inclusion or exclusion criteria at screening or baseline that may affect facial skin assessments.
- Non-compliance with assigned treatment regimen.
- Use of prohibited treatment or medication before or during the study,

Document Name	Statistical Analysis CCI	207468.docx	
Type	Version	Document Identifier	Effective Date
eldo_clinical_doc	1.0; CURRENT; Most-Recent; Effective	090032d580d23463	10-Apr-2017 13:34:23
Reason For Issue	Auto Issue		

which it is felt will affect facial skin assessments.

Violations will be documented in the Population Definitions document. The content of this document will be agreed upon between the Biostatistician and Clinical Development Director or designee prior to database lock and breaking of the study blind.

A PP analysis will be performed on the primary and key secondary objective if there is more than 10% difference in the number of subjects evaluable in any of the treatment groups for the ITT and PP populations.

## 5.2 Subgroups/Stratification

There was no stratification in this study.

## 5.3 Time Windows

All data will be accepted for analysis. Deviations from the scheduled nominal visit days are not expected. Any deviations will be noted in the deviation log and visits may be considered for exclusion from the Per Protocol population.

## 5.4 Missing Data Handling

Missing data will not be imputed. Dropouts will be included in analyses up to the point of discontinuation.

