### 8.1 Primary Analysis

The primary endpoint of the study will be change from baseline in Derma TOP parameter  $R_a$  at 4 weeks.

Baseline and change from baseline in DermaTOP parameters  $R_a$ ,  $R_z$ ,  $S_a$  and  $S_{tm}$  will be summarised (N, mean, standard deviation, median, minimum and maximum) by treatment arm (test product, Olay ProX Wrinkle Smoothing Cream, no treatment) for each study visit (weeks 2 and 4). For each parameter, test product versus no treatment and positive control versus no treatment will be compared for the change from baseline at 2 weeks, and 4 weeks, using analysis of covariance (ANCOVA) with subject (random effect), treatment, and side of face as main effects and baseline value as covariate. This approach allows for the inclusion of data from all subjects treated with a given treatment arm (test product, positive control or no treatment) regardless of the treatment group (test product/no treatment, test product/positive control, positive control/no treatment) to which they were randomised to derive estimates of treatment effect.

If the assumption of normality is rejected, an appropriate transformation to the data

Document Name	Statistical Analysis CCI	207468.docx	
Type	Version	Document Identifier	Effective Date
eldo_clinical_doc	1.0; CURRENT; Most-Recent; Effective	090032d580d23463	10-Apr-2017 13:34:23
Reason For Issue	Auto Issue		

may be performed to facilitate the above method of analysis. Least square means from the ANCOVA model for the change from baseline will be presented for each treatment arm and pairwise treatment comparisons, together with the 95% confidence intervals. In the absence of an appropriate data transformation, non-parametric analyses may be performed. In the event of the use of non-parametric analysis, median differences will be presented, together with 95% confidence intervals based on the Hodges-Lehmann method.

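### Subjects who withdraw after Day 15 are in ITT but add nothing to the primary Day 29 R_a contrast; a joint Day 15 and Day 29 model would use their data and be valid if dropout is missing at random (MAR)

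*SAP*

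**What the plan says.** The ITT population consists of randomised subjects who "have at least one post-baseline clinical assessment available. All efficacy analyses will be based on the ITT population" (SAP 5.1). Day 15 alone meets this.

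On missing data the two documents agree. Protocol 9.2.4 says "Missing data will not be replaced or imputed", and SAP 5.4 says "Missing data will not be imputed. Dropouts will be included in analyses up to the point of discontinuation".

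SAP 8.1 compares treatments at 2 and 4 weeks "using analysis of covariance (ANCOVA) with subject (random effect), treatment, and side of face as main effects and baseline value as covariate". The footnotes to the table shells in SAP Appendix 3 repeat these terms. No visit or treatment-by-visit term appears. The primary table is the R_a change at 4 weeks in the ITT population (SAP 11 and Appendix 2).

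The plan expects some loss: "Approximately 90 healthy subjects will be screened to randomise at least 72 subjects to ensure 66 subjects complete the entire study" (SAP 4). Withdrawn subjects are not replaced (Protocol 4.5). Neither document states a missingness assumption or a missing-data sensitivity analysis. The per-protocol population is a subset of ITT, so it cannot recover these subjects.

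**The concern.** A table labelled ITT would in fact contain only subjects measured at Day 29. For someone who leaves between the visits, the Day 15 change on both half-faces is known but plays no part in the primary result.

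The split face protects against general reasons for leaving, because a withdrawal removes both treatments together. It does not protect against reasons tied to one side. Such reasons are possible here. Only the evaluator is blinded, the product labels state the side of application (Protocol 5.9), all subjects report sensitive skin (Protocol 4.1), and adverse event and withdrawal of consent are listed reasons for stopping (Protocol 6.4).

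The success rule asks only for a trend in favour of the test product (SAP 8), so a shift of a fraction of a standard error could matter to the reading of the result.

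**Working it through.** **1. Who is in the Day 29 model.** From SAP 4, 72 − 66 = 6 subjects, and 6/72 = 8.3%. Also 66/(1 − 6/72) = 72, so the plan's figures agree. The shell for Table 9.3.2.2 asks for three contrasts at Day 15 and three at Day 29. A model with only subject, treatment, side and baseline gives one set of contrasts, so it has to be fitted once per visit. The documents do not say this in words; it follows from the missing visit term.

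**2. The plan's power figure.** SAP 4 says that with 40 subjects a difference of "at least 46% of the magnitude of the within-subject standard deviation of the difference" "would be detectable at two-sided alpha=0.05 with approximately 80% power". For a paired t-test the noncentrality is 0.46 × √40 = 2.909 on 39 df, which gives power of 81.0%. The figure reproduces. All sizes below are in SDs of the within-subject difference, with a true Day 29 effect of 0.46.

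**3. Set-up and assumptions.** The simulations used 72 subjects, 24 per treatment pair, with 6 lost after Day 15 and 1,500 or 3,000 trials per scenario (simulation error about 0.004). The documents do not give the following, so they are assumed:
- Day 15 to Day 29 correlation ρ of 0.3 to 0.9;
- equal between- and within-subject variance;
- a Day 15 effect of 65% to 70% of the Day 29 effect;
- all 6 losses after Day 15.

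Side and baseline terms were left out, and the covariance was taken as known except in step 7.

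Check on the standard error (SE): with no dropout, the precision is 24 (direct pairs) + 12 (through the positive control, 1/(1/24 + 1/24)) + 4 (between subjects) = 40, so SE = 1/√40 = 0.158. With 6 lost evenly, 0.158 × √(72/66) = 0.165. Both match the simulation.

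**4. Overstatement of the test effect at Day 29.**

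| Why the 6 leave | Per-visit ANCOVA | Joint model |
|---|---|---|
| At random | none | none |
| Worst two-side average at Day 15 (ρ 0.5; 0.8) | within 0.007 of zero | not run |
| Three for a poor test side, three at random (ρ 0.5 to 0.8) | 0.034 to 0.061 | not run |
| Partly driven by the side difference (ρ 0.5 to 0.8) | 0.034 to 0.054 | not run |
| Test side worst at Day 15 (ρ 0.5) | 0.067 to 0.073 | 0.005 or less |
| Test side worst at Day 15 (ρ 0.8) | 0.102 to 0.113 | 0.005 or less |
| Worst side difference plus noise, all 6 from test/no treatment (ρ 0.5; 0.7) | 0.073; 0.105 | about 0 |
| Worst side difference, all 6 from test/no treatment (ρ 0.5; 0.7) | 0.111; 0.149 | about 0 |

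In the last scenario ρ = 0.9 gives 0.191.

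**5. Hand check of the last row, ρ = 0.5.** The lowest quarter of a normal distribution lies on average 1.271 SD below the mean. Losing 6 of 24 leaves 18 subjects whose Day 15 difference is 6 × 1.271/18 = 0.424 SD too high, and 0.5 × 0.424 = 0.212 SD too high at Day 29. The direct comparison has weight 18/(18 + 12 + 4) = 0.529. The product is 0.112, against 0.111 simulated. The bias is thus weight × ρ × shift in the side difference. When withdrawal follows the two-side average, that shift is zero, which is why the second row shows essentially nothing.

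**6. Dropout that depends on the unseen Day 29 value (missing not at random, MNAR).** With all 6 from test/no treatment and ρ = 0.5, the bias is 0.220 per visit and 0.167 jointly: 0.167/0.220 = 76% remains. The share that remains is close to 1 − ρ², which is 75% at ρ = 0.5. At ρ = 0.9 it is 0.039/0.212 = 18%, against 19% from the formula.

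**7. Precision, and the joint model with estimated covariance.** Under random dropout the SE is 0.165 per visit and 0.160 to 0.165 jointly. A separate simulation with the covariance estimated from the data, and dropout following the Day 15 side difference, gave a bias of about 0.05 to 0.15 per visit and within about 0.02 jointly. Under random dropout the joint model lost no precision. Under MNAR dropout at ρ = 0.5 the bias fell only from 0.19 to 0.15.

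**The case against.** The strongest reply is that the plan is consistent and open. Dropouts do count up to discontinuation, because they enter the Week 2 analysis, and the table shells report missing counts by visit. Only about 6 subjects are at stake, in a proof-of-concept study that treats p-values mainly as summary statistics. The joint model also needs a richer covariance structure, and extending it to the 9-point Fitzpatrick score is not tested here. All of this stands, and it limits the weight of the point.

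Three stronger readings are tempting, and the documents support none of them:
- *The joint model removes dropout bias.* It does so only if dropout depends on baseline and Day 15 data and the model is correctly specified (steps 4 and 6). Under random dropout there is no bias to remove.
- *Any link between withdrawal and Day 15 response biases the result.* Only a link to the difference between sides, or to one product's side, does so to any material extent. Conversely, dropout driven by unseen Day 29 values can bias the result even when it is unrelated to Day 15.
- *The bias favours the test product.* No passage says who will leave. Dissatisfaction with the positive control or with the untreated side is as possible.

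**Conclusion.** The point holds as a gap in the primary analysis. A subject lost after Day 15 is labelled ITT and contributes nothing at Day 29, although half of that subject's post-baseline data exist. This follows from the text and needs no simulation.

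Whether it produces bias depends on why subjects leave. In the near-worst case of 6 withdrawals driven by a poor test side, the overstatement is about 0.07 to 0.15 SD. That is 0.07/0.46 = 15% to 0.15/0.46 = 33% of the planning effect, or 0.07/0.165 = 0.4 to 0.15/0.165 = 0.9 of a standard error. Milder side-related mechanisms give about 0.03 to 0.10 SD. Random dropout, or dropout tied only to overall response, gives essentially none. These sizes rest on the assumed visit correlation and on all 6 losses falling after Day 15. They shrink if fewer leave.

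The SAP should make the change because it is cheap and uses data already scheduled. The trial does not stand or fall on it.

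**What to change.** In SAP 8.1 and 5.4, fit the Day 15 and Day 29 changes in one mixed model:
- fixed effects: treatment, visit, treatment-by-visit, side, side-by-visit, baseline and baseline-by-visit;
- random subject, with half-face within subject correlated across visits.

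Keep Day 29 test product versus no treatment as the primary contrast. State that the model is valid if dropout depends only on baseline and Day 15 data (MAR), and that under MNAR it reduces the bias but does not remove it. Keep the per-visit ANCOVA as a sensitivity analysis. A delta-adjusted MNAR sensitivity analysis is an optional addition. Pre-specify a simpler covariance structure as fallback in case of non-convergence.

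The cost is SAP wording and a few lines of code before unblinding, plus a somewhat more complex covariance model. No new data are needed. With no dropout the Day 29 estimate is essentially unchanged. The SAP has already been amended to add a pre-unblinding step for adverse events, so a route for the change exists.
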